## Protocol Body

### 1.0 Objectives

1.1 To determine the efficacy and toxicity of radiation therapy alone in treating stage 1 and 2 MALT lymphoma for newly diagnosed patients and for the patients who failed other treatment modalities.

### 2.0 Background

2.1 Rationale- MALT lymphoma is a relatively recently described entity which is also known as extranodal marginal zone lymphoma (1)(2)(3)(4). It was initially recognized in gastrointestinal tract with the majority arising from the stomach. Nowadays, however, about 30 to 40% of the MALT lymphomas are thought to be of non-gastrointestinal origin according to the M.D. Anderson Cancer Center lymphoma data base and others (5). Though MALT lymphoma constitute about 7 to 8%(6) of non-Hodgkin's lymphoma, prospective clinical trials are scarce and optimal treatments still remain to be defined. It is generally considered to be a low grade lymphoma at early state (7)(8) having a very favorable prognosis even after localized treatments such as radiation therapy or surgical resection alone (9)(10). Most of the data on the treatments of MALT lymphoma come from experiences in gastric MALT lymphoma (11)(12)(13). There have been multiple retrospective series suggestive of favorable outcome for these patients. However, the first report on a prospective clinical trial in managing Ann Arbor stage 1 and 2 gastric MALT lymphoma with radiation therapy alone was published in 1998 and has been recently updated (14)(15). Twenty nine patients were treated with a median dose of 30 Gy (range 22.5 to 43.5) delivered at 1.5 Gy per fraction to the stomach and adjacent lymph nodes. At a median follow-up of 30 months, 94 % remain disease free. Non-gastric MALT lymphomas (16) (3)(5) have been reported in sites such as bowel (17) lung (18), breast (19)(20), skin (21), thyroid gland (22), bladder (23)(24), liver (25) dura (26)(27), esophagus (28) ocular adnexa (29)(30) along with other head and neck series limited by a small number of patients treated in a variety of different ways including any combination of chemotherapy, radiation therapy and surgery, thus yielding no significant insights into the optimal treatment except for the impression that most of them are very localized disease with favorable prognosis probably comparable to that of gastric MALT lymphoma (7). Therefore, we propose to prospectively study the efficacy and toxicity of radiation treatment for patients with stage 1 and 2 non-gastric MALT lymphoma as well as to verify the Memorial Sloan-Kettering Cancer Center data on gastric MALT lymphoma. Of note, a recent publication from the Non-Hodgkin's Lymphoma Classification Project reported an overall failure free survival of about 70% or higher if the International Prognostic Index is less than 4 in their retrospective analysis of 72 patients with stage 1 to 4 MALT lymphoma (33). Zinzani et al reported 5 year treatment failure rate of 70% for their review of 47 patients with stage 1 and 2 non-gastric MALT lymphoma(16). Based on the failure free survival curves presented in these studies, we believe it is a very reasonable hypothesis to test 75% or higher relapse free survival at 5 years with the majority of the relapses occurring within the first 5 years in our group of patients.

The data on the outcomes of the patients who relapse after initial treatment are lacking. The same statistical analysis and stopping rule will apply to the patients who are enrolled in this protocol after failure to initial treatment, though this may be very stringent criteria for this patient population.

2.2 Preliminary Data- We have recently reported our experience with 39 consecutive patients with MALT lymphoma with supradiaphragmatic presentation seen at M.D. Anderson Cancer Center between 1991 and 1997 (34). Ten of them were treated with radiation therapy alone. Two of them had stage 2 disease. The median dose was 39.6 Gy at 1.5 to 2.0 Gy per fraction. Everyone achieved a clinical complete response. At a median follow-up of 26 months, everyone is alive. Two patients experienced recurrence. Both of the recurrences were in the stomach. They were successfully salvaged, rendering every patient free of disease at the last follow-up. Of note is six of these 10 patients had primary conjunctiva lymphoma making the scope of this experience quite limited. We now propose to extend radiation treatment as the only modality to stage 1 and 2 non-gastric MALT lymphomas in general.

### 3.0 Background Drug Information

Cytotoxic drugs are not a planned part of treatment in this protocol.

### 4.0 Patient Eligibility

#### 4.1 Inclusion Criteria

- 4.1.1 Patients with newly diagnosed stage 1 and 2 MALT lymphoma are eligible for this study.
- 4.1.2 Patients with H. pylori positive gastric MALT lymphoma are recommended to have treatments with antibiotics prior to enrollment to this protocol.
- 4.1.3 Patients who failed other treatment modalities (e.g. chemotherapy, antibiotics therapy etc) are also eligible as far as they never had stage 3 or 4 disease during the course of the disease or disease progression to the opposite side of the diaphragm. (As the time course of the response to antibiotic therapy can be very variable among patients, sometimes requiring more than one year for complete response, failure to antibiotic therapy can be very variable among patients, sometimes requiring more than one year for complete response, failure to antibiotic treatment will be defined as no response or progression of the disease documented by endoscopy and biopsy.)
- 4.1.4 Patients who have had stage 4 diseases due to bilateral parotid gland or ocular/ocular adnexal involvement or due to multiple sites within Waldeyer's ring will still be eligible.

#### 4.2 Exclusion Criteria

- 4.2.1 Patients who had previous radiation dose to the site of the current primary disease which would lead to violation of known radiation tolerance limit of that particular site if treated again.
- 4.2.2 Patients with MALT lymphoma of the skin whose lesions are separated by more than 5 cm will be ineligible.

4.2.3 Previous or concurrent malignancy in any form would not be an exclusion criterion. However, patients who receive chemotherapy for concurrent malignancy will be excluded from statistical analysis.

4.2.4 Low blood cell counts would not be exclusion criteria as far as the patient is willing to accept supportive measures such as transfusions, filgrastim and epoetin.

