2)  $\geq 50\%$  increase in greatest diameter of any previously identified node greater than 1 cm its short axis or in the SPD of more than one node.

**Progressive disease** (PR, nonresponders) – 1)  $\geq 50\%$  increase from nadir in the SPD of any previously identified abnormal node for PRs or nonresponders. 2) Appearance of any new lesion during or at the end of therapy.

b. Response Assessment

Response is assessed on the basis of clinical radiologic, and pathologic (i.e, bone marrow) criteria. CT scans remain the standard for evaluation of nodal disease. Thoracic, abdominal, and pelvic CT scans are recommended even if those areas were not initially involved because of the unpredictable pattern of recurrence.

A bone marrow aspirate and biopsy should only be performed to confirm a CR if it is clinically indicated by new abnormalities in the peripheral blood counts or blood smear.

c. Response durations are measured from the time of response (not the beginning of treatment) until there is evidence of progressive disease. Progression free survival will be measured from protocol entry.

8.3 Frequency of Response Determination: All lesions must be measured at baseline and then as per section 7.4

8.4 Survival Durations: The survival of patients will be measured from entry into protocol.

8.5 All toxicities encountered during the study will be evaluated according to the grading system (0-4) in Appendix C. Duration and treatment will be recorded. Life-threatening toxicities should be reported immediately to the study chairman who in turn must notify the IRB. Should this occur, it will mandate closure of the protocol to patient entry for investigation as to the reasons for this and a decision can be taken as to whether the protocol can remain open or should be closed.

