## 11.0 Statistical Considerations and Stopping Rules

This is a trial to estimate the relapse-free survival rate (RFS) of patients with gastric and non-gastric MALT lymphoma treated with radiation therapy alone. Patient accrual is expected to be 10 – 15 per year for gastric and 5 – 10 per year for non-gastric MALT lymphoma at initial presentation. Accrual of less than 5 patients per year for either gastric or non-gastric MALT lymphoma is expected for presentation upon failure of other treatment modalities. The patient accrual and outcome analyses will be done separately in the following 4 groups: Gastric vs non-gastric MALT at initial presentation vs upon failure to other treatment(s).

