#### Accrual goals

The accrual goals for the patients at initial presentation are 40 for gastric and 35 for non-gastric MALT lymphoma. Based on the expectation that the relapse rate after radiation therapy alone will be 25% and that 70% of the relapsing patients will fail within 5 years, these numbers will provide a 95% confidence bound of +/- 5.9% for estimating the 2-year RFS. This calculation assumes that RFS follows an exponential distribution and we will follow all patients for at least 2 years.

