#### Stopping Rules for patient accrual at initial presentation

Based on the expectation that the relapse rate after radiation therapy alone will be 25% or less, RFS will be evaluated in each of the two subgroups of previously untreated patients and accrual stopped in RFS is < 70% after the first 15, 30, or 45 patients have been followed for a minimum of 2-years. Assuming that 70% of the relapsing patients will fail within 5 years, computer simulations indicate that this stopping rule will terminate patient accrual in both the gastric and non-gastric arms of the trial with a probability of 1% if the relapse rate is 25% with a 17% probability if the relapse rate is 50%, and with a probability of 60% if the relapse rate is 75%.

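### Section 4.2.3 drops patients from the analysis for chemotherapy given at any time, so a relapse already observed can be discarded; the likely effect is small and the remedy is a change of wording

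*Combined protocol and SAP*

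**What the plan says.** Section 4.2.3 has two parts. The first keeps entry open: "Previous or concurrent malignancy in any form would not be an exclusion criterion". The second acts on the analysis: "patients who receive chemotherapy for concurrent malignancy will be excluded from statistical analysis". The section does not define concurrent, does not say whether the chemotherapy must be under way or planned at entry, and does not offer censoring as an alternative.

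The reason for the rule is easy to see. The objective in Section 1.0 is "To determine the efficacy and toxicity of radiation therapy alone in treating stage 1 and 2 MALT lymphoma", and Section 3.0 states "Cytotoxic drugs are not a planned part of treatment in this protocol".

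Section 11.0 makes RFS the quantity of interest: "This is a trial to estimate the relapse-free survival rate (RFS) of patients". The four groups are analysed separately, with accrual goals of 40 gastric and 35 non-gastric patients at initial presentation. In each of those two groups the stopping rule has "accrual stopped in RFS is < 70% after the first 15, 30, or 45 patients" have at least 2 years of follow-up. Section 11.0 does not say whether patients removed under 4.2.3 count towards 15, 30 or 45.

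**The concern.** A rule that removes patients for a fact known at entry defines a population. A rule that removes them for something that happens later makes the analysis set depend on the course of follow-up. Even if the other cancer is present at entry, its chemotherapy may begin months after the radiation. A patient could relapse, then start chemotherapy for the other cancer, and both the patient and the relapse would leave the RFS estimate. A patient who stays free of relapse until the chemotherapy starts would also be lost, along with valid relapse-free time. The first loss raises RFS and the second lowers it.

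The groups are small and few relapses are expected by 2 years, so single patients carry visible weight, both in the estimate and at the first stopping look.

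**Working it through.** **Inputs** (Section 11.0): relapse rate 25%; "70% of the relapsing patients will fail within 5 years"; goals of 40 and 35; stop if RFS is below 70% at 15, 30 or 45 patients; stated stopping probabilities of 1%, 17% and 60% at relapse rates of 25%, 50% and 75%. The number of patients who would be excluded is not given. Deaths are not modelled.

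**1. Reproduce the plan's stopping probabilities.** Take relapse times among relapsing patients as exponential.
- Rate: -ln(0.3)/5 = 0.2408 per year.
- Share of relapses by 2 years: 1 - exp(-2 × 0.2408) = 0.382.
- Chance of relapse by 2 years at relapse rates of 25/50/75%: 0.0955, 0.1911, 0.2866.
- RFS below 70% means at least 5 of 15, 10 of 30 or 14 of 45 relapsed.
- Exact probability of stopping at any look, per group: 1.1%, 16.5%, 59.2%.

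This agrees with the plan's 1%, 17% and 60%, so the model is a fair basis for what follows.

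**2. Expected relapses and precision.** There are two readings of the exponential assumption.
- Relapsing patients exponential: 2-year RFS = 1 - 0.0955 = 90.4%. Expected relapses are 40 × 0.0955 = 3.8 and 35 × 0.0955 = 3.3. Half-width 1.96 × sqrt(p(1-p)/n) = 9.1 points (n = 40) and 9.7 points (n = 35).
- RFS itself exponential, with 0.25 × 0.70 = 17.5% relapsed by 5 years: 2-year RFS = 0.825^(2/5) = 92.6%. Expected relapses are 3.0 and 2.6, and half-widths are 8.1 and 8.7 points. With both groups pooled (n = 75) this reading gives 5.9 points, the plan's stated bound.

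Either way the half-width per group is about 8 to 10 points.

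**3. Effect of one exclusion on 2-year RFS.**

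| Group | All patients | One relapsed patient dropped | One relapse-free patient dropped |
|---|---|---|---|
| 40, 4 relapses | 36/40 = 90.0% | 36/39 = 92.3% (+2.3) | 35/39 = 89.7% (-0.3) |
| 35, 3 relapses | 32/35 = 91.4% | 32/34 = 94.1% (+2.7) | 31/34 = 91.2% (-0.3) |

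**4. Effect at the 15-patient look**, with excluded patients not replaced (an assumption, since the plan is silent).
- 5 relapses: 10/15 = 66.7%, stop. Drop one relapsed patient: 10/14 = 71.4%, continue.
- 4 relapses: 11/15 = 73.3%, continue. Drop two relapse-free patients: 9/13 = 69.2%, stop.

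The decision can therefore be altered in either direction.

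**5. How often the first reversal could occur.** Exactly 5 relapses in 15 has probability 0.9%, 9.2% and 19.8% at relapse rates of 25%, 50% and 75%. Suppose one patient in the 15, chosen at random, is always excluded. The chance that this patient is one of the 5 is 5/15, so the joint probability is about 0.3%, 3% and 7%.

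**6. Which looks can still affect accrual.** A look at k patients falls k/rate + 2 years after the start, at the accrual rates in Section 11.0.

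| Group (rate per year) | Accrual complete | 15-patient look | 30-patient look |
|---|---|---|---|
| Gastric (10 to 15) | 4.0 to 2.7 years | 3.5 to 3.0 years | 5.0 to 4.0 years |
| Non-gastric (5 to 10) | 7.0 to 3.5 years | 5.0 to 3.5 years | 8.0 to 5.0 years |

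The 15-patient look comes before accrual is complete only towards the slower rates. At the slowest rates 35 of 40 gastric and 25 of 35 non-gastric patients are already enrolled. The 30-patient look comes after accrual is complete, and 45 exceeds both goals.

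**The case against.** The strongest reply is that 4.2.3 stands among the entry criteria, that concurrent most naturally means present at entry, and that setting aside patients given systemic chemotherapy is a pre-specified and sensible way to isolate radiation alone. The motive stands. The reading does not settle the matter, because a cancer present at entry may be treated with chemotherapy later, and the sentence turns on receiving the chemotherapy. If only chemotherapy known at entry was meant, one clause would say so.

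The second reply is that the effect is minor. That also stands: the shifts lie well inside the confidence interval, and the reversal at 15 patients is rare at the design relapse rate.

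Three stronger readings are tempting and are not supported:
- A reader might infer that the rule inflates RFS. It can, but dropping relapse-free patients pulls the other way, and nothing in the documents fixes the balance.
- A reader might infer that the 30-patient look is equally exposed: 9 relapses in 30 is 70.0% (continue), while 9 in 29 is 69.0% (stop). The arithmetic is right, but at the stated accrual rates enrolment is already complete by then, so accrual is unaffected.
- A reader might infer that toxicity data vanish. Section 8.5 has all toxicities graded and recorded, Section 12.1 requires Grade 4 or 5 events to be reported, and Section 11.0 has no toxicity stopping rule. At most, these patients would be missing from a toxicity summary if that counts as statistical analysis.

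**Conclusion.** The concern holds in a limited form. As worded, 4.2.3 lets an event after entry decide who is analysed, and a relapse observed before that event would be discarded. The direction of bias is not fixed.

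The size is about -0.3 to +2.7 points of 2-year RFS per excluded patient, against a half-width of about 8 to 10 points, with an occasional reversal at the 15-patient look. These figures rest on the plan's relapse rate and timing, on complete 2-year follow-up without deaths, and on excluded patients not being replaced. How many patients would be affected is unknown and may be none. The point merits consideration because the change is cheap, not because the estimate is at serious risk.

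**What to change.** Reword 4.2.3, with a matching sentence in Section 11.0:
- Limit the exclusion to patients already receiving, or committed to, chemotherapy for another malignancy at entry. List them separately and do not count them in the 15, 30 or 45.
- Keep every other patient who starts radiation in the analysis. Count relapse and toxicity up to the start of any chemotherapy for the other malignancy, and censor RFS at that date.
- Report the present exclusion as a sensitivity analysis.

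This still serves the radiation-alone objective, because time after the chemotherapy starts does not enter RFS. In the 5-of-15 example, a relapse seen before the chemotherapy would remain an event and the result would stay at 66.7%.

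The cost is a few sentences and no extra patients. Where someone is censored before 2 years, RFS at a look needs an estimate that allows for censoring, such as Kaplan-Meier, in place of a simple proportion. The downside is that censoring at the start of chemotherapy may be informative, which is why the sensitivity analysis is needed.

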## 5.0 Treatment Plan

5.1 Radiation treatment will consist of involved field radiation therapy to primary site and adjacent lymphatics (if indicated). Initial fields to encompass the tumor site and the suspected microscopic disease will be taken to 30 to 30.6 Gy. Boost to the gross disease to 36 is indicated in some patients when tumor is larger than 5 cm. The only exception would be orbital or ocular adnexal lymphoma which may be treated to the final dose of 30 Gy or 30.6 Gy.

a) CT Planning is required for every patient unless it is technically not feasible. The only exception would be MALT lymphoma of the skin which may be treated with electron beams.

b) Though involved field radiation therapy to stomach only is recommended for stage 1 gastric MALT lymphoma, generous fields to encompass the peri-gastric and celiac lymph nodes are recommended if the patient presents with recurrent or refractory disease after chemotherapy. Every attempt needs to be made to preserve the function of the left kidney by using oblique fields after the initial AP-PA fields are taken to the kidney tolerance. The gastric fields need to be simulated and treated with empty stomach for optimum reproducibility.

## 6.0 Pretreatment evaluation

See Appendix A

6.1 A complete history and physical examination including performance status (Appendix B)

6.2 Laboratory studies will include a CBC with differential, platelet count, electrolytes, biochemical survey, TSH (if indicated due to the site of the disease), and beta-2 microglobulin. Imaging studies will include PA and lateral chest roentgenograms, CT of the neck, chest, abdomen, and pelvis. Esophogogastroduodenoscopy (EGD) needs to be done for every patient. If EGD is positive, colonoscopy along with small bowel series will be performed. Unilateral bone marrow biopsies will be obtained prior to initiation of therapy.

6.3 Location, type and size of all measurable lesions must be recorded prior to treatment.

## 7.0 Evaluation During and After Treatment

(See Appendix A)

7.1 Patients will be followed while on treatment with CBC with differential and platelet count only as clinically indicated. These will be also obtained at the follow-up visits.

7.2 A biochemical survey will be performed before radiation therapy and at the follow-up visits.

7.3 All initially abnormal imaging studies and endoscopies will be performed 3 months after completion of radiation therapy and yearly thereafter. Additional studies will be obtained only if indicated by the interval history and physical examination.

7.4 The follow-up visits will be done between 6 weeks to two months, and then every 3-4 months for the first year, every 4-6 months for the second year, every 6 months for the third & fourth year, and once a year thereafter or as per physician's discretion.

Please note: The post-treatment lab test and follow-up visits can be done less often (than previously stated) depending on the clinical judgment of the physicians.

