### 8.1 Tumor Measurements

- a. Lesions will be measured in centimeters prior to the course of therapy.
- b. The longest diameter and its perpendicular will be measured for bi-dimensionally measured lesion. Size will be reported as the product of the diameters.
- c. Measurements should be made and recorded by the physician.
- d. An estimate of overall objective and subjective response will be made and recorded at each visit.
- e. Endoscopy findings will be mapped out.

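### Section 7.3 schedules no imaging or endoscopy in the 9 months before 2 years from the end of radiation, so relapses that visits miss, if dated at detection, bias 2-year RFS upward by 0 to about 3 points at the design relapse rate

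*Combined protocol and SAP*

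**What the plan says.** On assessment, section 7.3 states: "All initially abnormal imaging studies and endoscopies will be performed 3 months after completion of radiation therapy and yearly thereafter". It adds: "Additional studies will be obtained only if indicated by the interval history and physical examination". Section 7.4 puts visits 4 to 6 months apart in year 2, and the note under it says that "follow-up visits can be done less often (than previously stated) depending on the clinical judgment of the physicians".

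Section 8 reads differently. Section 8.1d says: "An estimate of overall objective and subjective response will be made and recorded at each visit". Section 8.3 says: "All lesions must be measured at baseline and then as per section 7.4"; it names no modality. Section 8.2b recommends chest, abdominal and pelvic CT even for areas that were not involved at the start.

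On time origin, section 8.2c says: "Progression free survival will be measured from protocol entry". Section 8.4 gives the same origin for survival. Neither an origin for relapse-free survival (RFS) nor a rule for dating a relapse is given.

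Section 11.0 sets accrual goals of 40 gastric and 35 non-gastric patients at initial presentation, to be analysed separately, and a 95% bound of +/- 5.9% for 2-year RFS. Accrual in a group stops if RFS is below 70% once 15, 30 or 45 patients have at least two years of follow-up. The stated stopping probabilities are 1%, 17% and 60% at relapse rates of 25%, 50% and 75%.

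**The concern.** Read literally, section 7.3 puts scheduled studies at 3, 15 and 27 months after radiation. The last one before the 2-year mark comes 9 months early, and the next comes 3 months late. A relapse between months 15 and 24 that causes no symptoms and is not found at a visit is first seen at month 27. If it is dated then, the patient counts as relapse-free at 2 years, which is the time point for which section 11.0 states its precision. For the 2-year estimate this error runs only one way, in favour of radiation. It also bears on the stopping rule, because it grows with the relapse rate.

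**Working it through.** **Inputs.** Study times and visit intervals come from sections 7.3 and 7.4; group sizes, relapse rates, accrual rates and looks from section 11.0. Three things are assumed: radiation ends 0, 1.5 or 3 months after entry; scheduled rounds find every relapse to date; and visits find none, half or all of the relapses in the gap.

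**1. Reproduce the stated precision.** Take a plain exponential with 0.25 x 0.70 = 17.5% relapsed by 5 years. The hazard is -ln(0.825)/5 = 0.0385 per year, and 2-year RFS is exp(-2 x 0.0385) = 92.6%. The half-width 1.96 x sqrt(S(1-S)/n) is 5.93 points at n = 75, 8.1 at n = 40 and 8.7 at n = 35. The +/- 5.9% therefore belongs to the two groups pooled.

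**2. Reproduce the stated stopping probabilities.** Let a fraction R relapse, with exponential times among relapsers and 70% of them by 5 years. The rate is -ln(0.30)/5 = 0.2408 per year, and S(t) = 1 - R(1 - exp(-0.2408t)). With true 2-year status known for everyone and all three looks used, per-group stopping is 1.1%, 16.5% and 59.2%, matching 1%, 17% and 60%. Under this model 2-year RFS at R = 25% is 90.4%, with half-widths of 9.1 (n = 40) and 9.7 (n = 35).

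**3. Bias in 2-year RFS.** Let L be the time of the last scheduled study before 24 months, and m the share of relapses in the gap that visits miss. Then bias = m x [S(L) - S(24 months)]. At R = 25%:

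| Radiation ends after entry | L from entry | Visits find none | Half | All |
|---|---|---|---|---|
| 0 months | 15 months | 3.06 points | 1.53 | 0 |
| 1.5 months | 16.5 months | 2.51 points | 1.25 | 0 |
| 3 months | 18 months | 1.98 points | 0.99 | 0 |

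If visits find none, this is 0.7-1.1 patients of 35 or 0.8-1.2 of 40. The plain exponential of step 1 gives 2.7, 2.3 and 1.8 points. In the step 2 model the bias is proportional to R. If visits find none, it is therefore 2 x (1.98 to 3.06) = 4.0-6.1 points at 50% relapse and 3 x (1.98 to 3.06) = 5.9-9.2 at 75%.

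**4. Which looks can stop accrual?** With accrual a per year and goal N, the look at k patients comes at k/a + 2 years and accrual ends at N/a, assuming accrual is not paused.

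| Group, rate | 15-patient look | 30-patient look | Accrual ends | Left to enrol at the 15-patient look |
|---|---|---|---|---|
| Gastric, 10/year | 3.5 years | 5.0 | 4.0 | 5 |
| Gastric, 15/year | 3.0 | 4.0 | 2.7 | 0 |
| Non-gastric, 5/year | 5.0 | 8.0 | 7.0 | 10 |
| Non-gastric, 10/year | 3.5 | 5.0 | 3.5 | 0 |

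The 30-patient look always comes after accrual ends, and 45 exceeds both goals.

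**5. Stopping at the 15-patient look.** Stopping needs 5 or more relapses (10/15 = 67%; 11/15 = 73%). With true 2-year status the probabilities are about 1%, 14% and 44%. If RFS is read at 2 years from detection dates:

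- At 50% relapse it is 8-10% if visits find half and 4-6% if they find none.
- At 75% relapse it is 28-34% and 15-24%.

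If all follow-up is used and visits find none, simulation (40,000 trials, even entry, radiation ending at 1.5 months, 5 to 15 patients per year) gives 13-31% at 50% relapse and 42-73% at 75%.

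**The case against.** The strongest objection is that the gap rests on one side of a conflict. Section 8.3 ties lesion measurement to the 7.4 visits, and section 8.1d asks for a response estimate at each visit. If measurement means imaging, most of the gap closes for known lesions. Section 7.0 also refers to Appendix A, which could not be checked. Reading the yearly studies as 12 and 24 months after radiation would close the gap too, though the text more naturally counts from the 3-month study. This objection stands as a limit on the size, not as an answer. Sections 7.3 and 8.3 still disagree, and 7.3 is the one that speaks of imaging and endoscopy.

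A second objection is that the effect is small. Even in the worst case, ordinary Kaplan-Meier intervals on detection dates cover 89.5-94.2% in simulation, and only 3-4 relapses per group are expected by 2 years. That also stands, but the error is systematic and cheap to remove.

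A reader might infer that the gap necessarily weakens the stopping rule. The documents do not support this. They require two years of follow-up but do not say that RFS is read at 2 years. If all follow-up is used, stopping at the 15-patient look can exceed even the stated figures (step 5). The fall from 1/17/60% to 1/14/44% comes from looks that cannot stop accrual, not from the imaging gap.

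A reader might also infer a much larger bias from relapses at new sites. In the sponsor's radiation-alone series of ten supradiaphragmatic patients there were two recurrences: "Both of the recurrences were in the stomach". But the documents give no share of relapses at sites that would go unstudied, a repeated CT shows new lesions within its field, and section 8.2b recommends wider CT. No figure can be put on it. What remains is narrow. Baseline endoscopy of the upper gut (EGD) "needs to be done for every patient" under section 6.2, yet a patient whose EGD is normal has no scheduled repeat under 7.3.

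**Conclusion.** The concern holds in a limited form. Under section 7.3 no scheduled study falls in the 9 months before 2 years from the end of radiation, or in about the last 6-9 months before 2 years from entry. Relapses that visits miss there, if dated at detection, bias 2-year RFS upward by 0 to about 3 points at 25% relapse. That is at most about one patient per group and well inside the per-group half-width of 8-10 points.

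The size depends on the share of gap relapses that visits find (unknown), on dating at detection (the plan sets no rule), on the assumed end of radiation, and on section 7.3 rather than 8.3 governing. The effect on stopping has no fixed direction until the plan says how RFS is read at a look. Separately, the stated 1/17/60% rely on looks that cannot halt accrual. The point is worth fixing, but it does not threaten the trial's main conclusion at the design relapse rate.

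**What to change.** 1. State the RFS origin and the relapse-dating rule, and estimate 2-year RFS by an interval-censored method using last negative and first positive study dates. A simple form is a life table on the study rounds. A patient counts in a round only once its date has passed, and RFS at 2 years is read inside the 15-27 month interval under constant hazard. In simulation this leaves a bias of about 0.2 points or less. If round times differ between patients, a piecewise-exponential interval-censored likelihood does the same. The cost is a little more analysis work, reliance on constant hazard between 15 and 27 months, and up to about 1.3 points more sampling half-width if visits find no gap relapse. No new studies are needed.

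2. State whether RFS at a look is read at 2 years or over all follow-up. Restate the stopping probabilities under the actual assessment schedule, for a range of visit-detection shares, using only looks that can occur before accrual ends. With the 15-patient look alone and true 2-year status they are about 1/14/44%. They are lower if gap relapses are missed under the 2-year reading, and not necessarily lower over all follow-up. The cost is a rerun simulation and possibly less favourable figures; no look needs to be delayed.

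3. Reconcile section 7.3 with 7.4, 8.2b and 8.3, so that the studies on which RFS rests are the same throughout. The position of patients with a normal baseline EGD belongs here, because item 1 cannot recover relapses that no study looks for.
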